4. PARTICIPANT SELECTION AND WITHDRAWAL CRITERIA

4.1. Part 1 Study Population

Approximately 40 participants will be enrolled at approximately 13 investigational sites in North America and Europe. Two cohorts will be enrolled in Part 1 (Treatment Period):

- *GRN* mutation Cohort (up to 20 asymptomatic and symptomatic participants), including:
 - All asymptomatic and symptomatic participants in Study AL001-1 may be enrolled.
 - New symptomatic *GRN* mutation carriers may be enrolled.
- *C9orf72* mutation Cohort (up to 20 new symptomatic participants).

4.1.1. Inclusion Criteria – Part 1 (Treatment Period)

Prospective participants must meet all of the following criteria during the pre-study evaluation in order to be eligible to enroll in the study:

Part 1 (Treatment Period) Participant Category Inclusion Criteria:

1. Prospective participant meets all of the following criteria specific to their applicable participant category:

Participant Category 1: *GRN* Mutation Carriers, Symptomatic, from AL001-1

- Completed Study AL001-1 through the Day 57 visit and did not experience AEs that the investigator deems would prevent safe participation in Study AL001-2.
 - All previous participants in the AL001-1 study must be rescreened and meet all inclusion/exclusion criteria applicable to this study.
- Meets 1 or more of the 6 behavioral/cognitive symptoms required for a diagnosis of possible behavioral variant frontotemporal dementia (bvFTD; [Rascovsky 2011](#)), or has a diagnosis of PPA ([Gorno-Tempini 2011](#)).

Participant Category 2: *GRN* Mutation Carriers, Asymptomatic, from AL001-1

- Prospective participant completed Study AL001-1 through the Day 43 visit and did not experience AEs that the investigator deems would prevent safe participation in Study AL001-2.
 - All previous participants in the AL001-1 study must be rescreened and meet all inclusion/exclusion criteria applicable to this study. If a participant becomes symptomatic during or after Study AL001-1, they will be screened under Category 3 (symptomatic).

Participant Category 3: GRN Mutation Carriers, Symptomatic, New

- Is a carrier of a loss-of-function *GRN* mutation causative of FTD and knows their mutation status.
- Has a CDR® plus NACC FTLD global score of 0.5, 1, or 2; and 1 or more of the 6 behavioral/cognitive symptoms required for a diagnosis of possible bvFTD ([Rascovsky 2011](#)), or a diagnosis of PPA ([Gorno-Tempini 2011](#)).

Participant Category 4: C9orf72 Mutation Carriers, Symptomatic, New

- Is a carrier of a hexanucleotide repeat expansion *C9orf72* mutation causative of FTD and knows their mutation status.
- Has a CDR® plus NACC FTLD global score of 0.5, 1, or 2; and 1 or more of the 6 behavioral/cognitive symptoms required for a diagnosis of possible bvFTD ([Rascovsky 2011](#)), or a diagnosis of PPA ([Gorno-Tempini 2011](#)).

Part 1 (Treatment Period) General Inclusion Criteria:

2. 18 to 85 years of age, inclusive, at screening.
3. At screening, female prospective participants must be nonpregnant and nonlactating, and at least one of the following conditions must apply:
 - a. Not a woman of childbearing potential (WOCBP) (either surgically sterilized or physiologically incapable of becoming pregnant, or at least 1-year postmenopausal [amenorrhea duration of 12 consecutive months with no identified cause other than menopause]).
 - b. Is a WOCBP and using an acceptable contraceptive method from screening until 10 weeks after the last dose of study drug. Acceptable contraception is defined as using hormonal contraceptives or an intrauterine device combined with at least 1 of the following forms of contraception: a diaphragm or cervical cap, or a condom. In addition, total abstinence, in accordance with the lifestyle of the participant, is acceptable.
 - c. A WOCBP must have a serum pregnancy test conducted at screening. Additional requirements for pregnancy testing during and after the final dose of study treatment are located in the Schedules of Assessments ([Table 4](#), [Table 5](#), [Table 7](#), and [Table 9](#)).
4. Male prospective participants, if not surgically sterilized, must agree to use acceptable contraception and not donate sperm from Day 1 until 10 weeks after the last dose of study drug. Acceptable contraception for the male participant when having sexual intercourse with a WOCBP who is not currently pregnant is defined as using a condom. In addition, WOCBP partners must use hormonal contraceptives (e.g. combined oral contraceptive pill) or an intrauterine device combined. In addition, total abstinence, if in accordance with the usual lifestyle of the prospective participant, is acceptable. Vasectomized male participants should have received medical assessment of surgical success.
5. Agrees not to donate blood or blood products for transfusion for the duration of the study and for 1 year after final dose of study drug.

6. Is willing and has the ability to comply with the study protocol requirements, in the opinion of the investigator.
7. Is willing and able to give informed consent. If the study participant is not competent, a legally authorized representative must provide informed consent on their behalf, and the participant must provide assent, in accordance with the local regulations, guidelines, and institutional review board (IRB) or independent ethics committee (IEC).
8. Has availability of a person (“study partner”) who has frequent and sufficient contact with the participant (at least 5 hours per week of in-person contact), can provide accurate information regarding the participant’s cognitive and functional abilities as well as their health throughout the study, agrees to provide information at site visits that require partner input for COA completion, and signs the necessary consent form. (Note: asymptomatic participants require the study partner at the COA visits only; symptomatic participants require the study partner at each visit).
 - The study partner must have sufficient cognitive capacity to accurately report upon the participant’s behavior, cognitive, and functional abilities in the opinion of the investigator. The study partner should be in sufficiently good general health to have a high likelihood of maintaining the same level of interaction with the participant, and participation in study procedures throughout the study duration.
 - The same study partner should participate throughout the duration of Part 1 of the study. If a change in study partners during Part 1 is necessary, the Medical Monitor must be contacted.

Part 1 (Treatment Period) – Inclusion criteria applicable to those UK, US, or Canadian participants participating in the optional Winterlight Labs Speech Assessment (WLA) only:

1. Has available and willing study partner to administer the WLA.
2. Has WiFi access in their residence or WiFi access in a private area where the testing can take place.
3. US, UK, or Canadian participants and study partners must be proficient in English in the investigator’s opinion.

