3.3.2. Part 2 – Optional OLE

Eligibility Confirmation

There is no Screening period for participants that opt-in to continue receiving AL001 in Part 2 (Optional OLE) of the study. Participants who, after completing the 96-week treatment period in Part 1 (Week 97), and who provide informed consent to participate in Part 2 (optional OLE) and meet all the eligibility criteria for the OLE (prior to Week 101 study drug administration), may continue to receive their next regularly scheduled dose of AL001 according to the OLE administration schedule (continuation from Week 97 to Week 101).

Treatment Period and Follow-Up Period

The Part 2 OLE period will be up to 96 weeks. Study treatment (AL001 60 mg/kg) will be administered IV q4w for a total of up to 25 doses. Blood sampling for safety will be performed approximately every 12 weeks. Clinical outcome assessments, including those performed by the participant and their study partner, will be conducted approximately every 24 weeks. Imaging will be performed approximately every 48 weeks.

Participants who discontinue study treatment early (e.g., due to participant decision, withdrawal criteria, AL001 commercial availability in the country where the participant is being treated) will be followed for safety at 10 weeks after the last dose of AL001.

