4.2.1. Inclusion Criteria - Part 2 (Optional OLE)

The OLE is optional for participants who complete Part 1 of the study. Participants who complete Week 97 of Part 1 of the study are eligible for continued treatment with AL001, provided that all of the following criteria are met:

1. Participant is willing and able to give informed consent to continue treatment with AL001. If the study participant is not competent, a legally authorized representative must provide informed consent on their behalf, and the participant must provide assent, in accordance with the local regulations, guidelines, and institutional review board (IRB) or independent ethics committee (IEC).
2. Is willing and has the ability to comply with OLE requirements, in the opinion of the investigator.
3. Has availability of a person (“study partner”) who can continue to assist with assessments throughout the OLE evaluation period. The study partner must have frequent and sufficient contact with the participant (at least 5 hours per week of in-person contact), have the ability to provide accurate information regarding the participant’s cognitive and functional abilities as well as their health throughout the study, agree to provide information at site visits that require partner input for COA completion, and sign the necessary consent form. (Note: asymptomatic participants require the study partner at the COA visits only; symptomatic participants require the study partner at each visit).
 - The study partner must have sufficient cognitive capacity to accurately report upon the participant’s behavior, cognitive, and functional abilities. The study partner should be in sufficiently good general health to have a high likelihood of maintaining the same level of interaction with the participant, and participation in study procedures throughout the study duration.
 - The Part 2 study partner can be the same individual as in Part 1, or it can be a different individual, but the same Part 2 study partner should participate throughout the duration of Part 2. If a change in study partner during Part 2 is necessary, the Medical Monitor must be contacted.

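### Inclusion criterion 3 lists the screening pregnancy test as an alternative to contraception, so read literally its contraception rule excludes no one: a minor drafting error in a safety rule

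*Protocol*

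**What the plan says.** Protocol Section 4.1.1 opens by stating that "Prospective participants must meet all of the following criteria during the pre-study evaluation in order to be eligible to enroll in the study". General criterion 3 then governs women: "female prospective participants must be nonpregnant and nonlactating, and at least one of the following conditions must apply". Three items of equal rank follow.

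- Item a: the woman is not a WOCBP.
- Item b: "Is a WOCBP and using an acceptable contraceptive method from screening until 10 weeks after the last dose of study drug". The accepted methods are then listed, and abstinence is allowed.
- Item c: "A WOCBP must have a serum pregnancy test conducted at screening". It refers to Tables 4, 5, 7 and 9 for later testing.

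Footnote c to Table 3 and footnote j to Table 4 give the serum test at screening to all WOCBP.

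Criterion 4 covers men: "Male prospective participants, if not surgically sterilized, must agree to use acceptable contraception". It adds that "WOCBP partners must use hormonal contraceptives" or an intrauterine device. Surgically sterilized men are exempt, and abstinence is accepted.

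For Part 2, Section 3.3.2 says that "There is no Screening period for participants that opt-in to continue receiving AL001 in Part 2". Section 4.2.1 says that those who complete Week 97 "are eligible for continued treatment with AL001, provided that all of the following criteria are met". Neither the three criteria that follow nor the three exclusions in Section 4.2.2 mention contraception or pregnancy.

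**The concern.** Item c is a duty that falls on every WOCBP, but it sits in a list from which only one item need be true. A test that all WOCBP undergo then counts as an alternative to contraception, and item b stops working as an entry requirement.

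This matters because item b carries the whole load for female participants. I found no other contraception requirement for them in the rest of Section 4.1.1, the exclusions in 4.1.2, the withdrawal rules in 4.3.1.1 and 4.4.1, Section 7.12 on pregnancy, the Part 2 criteria or the SAP. The drug is an investigational antibody. WOCBP can plausibly enrol, since the age range starts at 18 and asymptomatic carriers are admitted.

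There is also a consequence for oversight. Protocol Section 12.4.2 and SAP Section 3.2 class failure to meet an entry criterion as a major deviation. Under the literal wording, enrolling a WOCBP who uses no contraception would not be a deviation and would not be flagged as one.

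**Working it through.** The plan gives no figure to reproduce, so the check is one of logic.

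**Inputs**

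- Connector inside criterion 3: at least one of a, b, c, in addition to being nonpregnant and nonlactating (Section 4.1.1).
- Connector between numbered criteria: all must be met (Section 4.1.1 lead-in). This joins criterion 3 to the others and does not alter the choice inside it.
- Test coverage: every WOCBP at screening (Table 3 footnote c, Table 4 footnote j).

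**Rules compared**, for nonpregnant, nonlactating women:

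- Literal: a or b or c.
- Intended: a or (b and c).

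| WOCBP | Contraception | Serum test | Literal | Intended |
|---|---|---|---|---|
| No | either | either | eligible | eligible |
| Yes | No | No | not eligible | not eligible |
| Yes | No | Yes | **eligible** | **not eligible** |
| Yes | Yes | No | **eligible** | **not eligible** |
| Yes | Yes | Yes | eligible | eligible |

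The two rules disagree in two rows. The row with contraception but no test should not arise, because every WOCBP is tested. With the test always done, three categories remain: not a WOCBP, WOCBP with contraception, WOCBP without. The literal rule admits 3 of 3 and the intended rule 2 of 3. Item c is then true for every WOCBP, so removing item b would change nobody's eligibility under the literal rule. This counts categories and does not estimate how many women are affected.

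**What limits the consequence**

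- The requirement to be nonpregnant stands outside the lettered list, so the literal reading does not admit a pregnant woman.
- Serum testing is done at screening. Urine tests are scheduled at Day 1 and at the dosing visits in Tables 4, 5, 7 and 8, before drug is given.
- Pregnancy is a reason to stop study drug (Sections 4.3.1.1, 4.4.1 and 7.12).

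These measures limit further exposure after conception. They do not prevent conception on treatment, which is the purpose of item b.

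**Cross-reference.** Table 9 has columns for vital signs, PK, ECG, ADA, progranulin and exploratory biomarkers, and none for pregnancy testing. The pregnancy-test row for Weeks 165 to 197, the Part 2 EOS visit and Safety Follow-up is in Table 8.

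**The case against.** The best defence is that nobody would read the criterion this way. Items a and b describe a woman's state, while item c is an instruction followed by a pointer to the schedules. Treating it as a condition that she satisfies also makes item b pointless, although item b specifies methods, duration and abstinence in detail. This argument stands as evidence of intent, and most sites would probably apply a or b plus the test. It does not make the text correct: the lead-in calls all three items conditions and asks for one of them.

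A second argument is that little can change now. The first participant was dosed on 27 September 2019 (Protocol Section 1.2.3), and SAP Section 2 already reports high attrition. Rewording an entry criterion may therefore screen few or no further women. That also stands, and it is why the site memo matters more than the amended sentence.

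Several stronger readings are tempting, and the documents do not support them.

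- *WOCBP without contraception have been enrolled.* Nothing in either document shows this.
- *Part 2 has no contraception rule.* Item b runs until ten weeks beyond the final dose of study drug. Section 3.3.1 defines study drug as AL001, and Section 5.1 gives AL001 in Part 2 as well. Properly read, item b already reaches the extension.
- *Women were deliberately held to a looser rule than men.* The detail in item b points the other way. Criterion 4 binds more directly, but it has its own exemptions and an unfinished phrase about the intrauterine device, so it is no model text.
- *The length of treatment, or the interval from last dose to Safety Follow-up, measures the harm.* Both come from the visit schedule and would be the same after rewording.

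**Conclusion.** This is a minor drafting error in a safety rule. As written, criterion 3 lets the universal screening test stand in for contraception, and item b excludes no one. The logic is certain; the practical effect is probably small.

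The number of women affected is unknown and may be zero. The documents do not give the number of WOCBP, who are some part of about 40 participants of both sexes aged 18 to 85. A reader might infer that pregnant women could be dosed or that the trial's results are at risk. Neither follows: pregnancy remains disqualifying, and no endpoint, sample size or analysis depends on this criterion.

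The statement that item b is the only contraception rule for female participants rests on the text available to me. I did not have the consent form, the Investigator's Brochure or the part of the protocol between Sections 1.3.2 and 1.3.3, and any of these could contain a further instruction.

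**What to change.** Reword the lead-in of criterion 3 to: *must be nonpregnant and nonlactating, and either a or b must apply*. Take item c out of the list and state the screening serum test as a separate requirement for every WOCBP. As a clerical correction, change its pointer from Table 9 to Table 8.

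Entry criteria act at the pre-study evaluation, so an amended sentence alone will not reach women already on treatment. Send sites a short memo confirming that item b continues to apply to WOCBP on treatment in Parts 1 and 2 until ten weeks beyond the final dose.

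The cost is one memo now and a minor amendment with IRB/IEC submission under Section 12.4.1. It adds no procedure or participant and changes no analysis.

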4.1.2. Exclusion Criteria - Part 1 (Treatment Period)

Prospective participants who meet any of the following criteria during the pre-study evaluation will be excluded from enrolling in the study:

1. History of severe allergic, anaphylactic, or other hypersensitivity reactions to chimeric, human, or humanized antibodies or fusion proteins.
2. History of substance use disorder (drug or alcohol) within 2 years prior to the first study drug administration, with the exception of nicotine, as defined by the Diagnostic and Statistical Manual of Mental Disorders, fifth edition criteria ([American Psychiatric Association 2013](#)).

3. Current acute illness or active infection requiring oral or IV antibiotics within 30 days prior to the first study drug administration that may affect safety assessments.
4. History of surgery or hospitalization during the 30 days prior to first study drug administration.
5. History of cancer within the last 5 years with the exception of basal cell or squamous cell carcinoma.
6. History or presence of intracranial tumor that is clinically relevant (e.g., glioma, cerebral metastasis).
7. Positive for hepatitis B surface antigen, hepatitis C virus antibodies, or human immunodeficiency virus-1 and -2 antibodies or antigen, or history of spirochetal infection of the CNS (e.g., syphilis or borreliosis).
8. Significant kidney disease as indicated by a screening creatinine clearance <30 mL/min as calculated by the central laboratory using the Cockcroft-Gault formula, which remains <30 mL/min if retested.
9. Impaired hepatic function as indicated by screening aspartate aminotransferase (AST) or alanine aminotransferase (ALT) $\geq 2.5 \times$ the upper limit of normal (ULN) or total bilirubin $\geq 1.5 \times$ ULN, which remains above either of these limits if retested or other abnormalities in synthetic function that are clinically significant. Note: Participants with Gilbert's syndrome are eligible to participate if approved by the Medical Monitor.
10. Unstable or clinically significant cardiovascular disease (e.g., myocardial infarction, angina pectoris, New York Heart Association Class III or more cardiac failure) within the last 2 years.
11. Uncontrolled hypertension, defined as an average systolic blood pressure ≥ 150 mmHg or an average diastolic blood pressure ≥ 95 mmHg, in an individual with hypertension.
12. History of or current abnormal ECG that is clinically significant, including atrial fibrillation, complete left bundle branch block, second- or third-degree atrioventricular block, or evidence of acute or subacute myocardial infarction or ischemia.
13. History of ventricular dysrhythmias or risk factors for ventricular dysrhythmias such as structural heart disease (e.g., severe left ventricular systolic dysfunction, left ventricular hypertrophy) or clinically significant electrolyte abnormalities (e.g., hypokalemia, hypomagnesemia, hypocalcemia). Note: Participants with premature ventricular contractions are eligible to participate.
14. Contraindication to lumbar dural puncture, including coagulopathy, concomitant anticoagulation (except for a platelet inhibitor such as aspirin), thrombocytopenia, or other factor that precludes safe lumbar puncture.
15. Dementia or a milder, symptomatic syndrome (e.g., mild cognitive impairment, mild behavioral impairment, or mild motor impairment) due to a condition other than FTD,

including, but not limited to, Alzheimer's disease, Parkinson's disease, dementia with Lewy bodies, Huntington disease, or vascular dementia.

16. History or presence of clinically evident vascular disease potentially affecting the brain (e.g., clinically significant carotid or vertebral artery stenosis or plaque; cerebral hemorrhage or infarct greater than 1 cm³; 3 or more lacunar infarcts in any location); cerebral contusion; encephalomalacia; intracranial aneurysm; arteriovenous malformation; subdural hematoma; hydrocephalus; space occupying lesions (e.g., abscess or brain tumor such as meningioma) that has the potential to affect cognitive function; or intracranial tumor that is clinically relevant (e.g., glioma, cerebral metastasis).
17. History of severe, clinically significant (persistent neurologic deficit or structural brain damage) CNS trauma.
18. Prospective participant resides in a skilled nursing facility, convalescent home, or long-term care facility at screening and requires continuous nursing care (i.e., >3 months). Participants from the Phase 1 study (AL001-1) who have since moved to one of these facilities and require continuous nursing care are not eligible to continue to this study (AL001-2).
19. Unable to tolerate MRI procedures (e.g., due to anxiety or claustrophobia) or has a contraindication to MRI, including, but not limited to, the presence of pacemakers, aneurysm clips, artificial heart valves, ear implants, or foreign metal objects in the eyes, skin, or body that are not compatible with an MRI scan; or any other clinical history or examination finding that would pose a potential hazard in combination with MRI.
20. Prospective participant has a medical condition or extenuating circumstance that, in the opinion of the investigator, might compromise his or her ability to comply with the protocol-required testing or procedures or compromise the participant's well-being, safety, or clinical interpretability.

Part 1 (Treatment Period) – Medication-Related Exclusion Criteria:

The following medications are prohibited for a prespecified duration prior to study start, as indicated, and during the entire period of study participation (participants who start these medications during the study may be withdrawn from study drug):

21. Cannabinoids, benzodiazepines, and tricyclic antidepressants are prohibited, unless prescribed as a stable regimen for at least 30 days prior to study drug administration or used as premedication prior to lumbar puncture or MRI procedures; however, use is not permitted within 8 hours before any COA.
22. Any stimulant medication (e.g., amphetamine, dextroamphetamine, dexmethylphenidate, lisdexamfetamine, methylphenidate) is prohibited unless prescribed as a stable regimen for at least 90 days prior to study drug administration.
23. Any passive immunotherapy (immunoglobulin) or other long-acting biologic agent that is under evaluation to prevent or postpone cognitive decline within 1 year of screening (participation in Study AL001-1 does not apply to this criterion).

24. Any experimental vaccine or gene therapy; routinely recommended vaccinations are allowed as well as any vaccine against SARS-CoV-2 administered under an Emergency Use Authorization.
25. A drug from a clinical study (other than AL001-1) within 30 days prior to drug administration in the current study (study drug administration); use of any experimental oral therapy within 30 days or 5 half-lives prior to study drug administration, whichever is greater; use of any biologic therapy within 90 days or 5 half-lives prior to study drug administration, whichever is greater; or any other investigational treatment within 5 half-lives or 90 days prior to study drug administration, whichever is longer.
26. Typical antipsychotic or neuroleptic medication within 6 months of study drug administration except as brief treatment for a nonpsychiatric indication (e.g., emesis).
 - a. Use of atypical antipsychotic medications or use of pimavanserin is allowed if treated with a stable regimen for at least 90 days prior to study drug administration.
27. Anti-coagulation (e.g., coumadin, heparinoids, apixaban) medications within 90 days of study drug administration. Note: Use of aspirin or antiplatelet medication is allowed.
28. Systemic immunosuppressive therapy or anticipated to be needed during the study.
 - a. Use of prednisone of ≤ 10 mg/day or an equivalent corticosteroid is allowed if stable for at least 90 days prior to study drug administration and hemoglobin >9 g/dL, white blood cell (WBC) count $>3000/\text{mm}^3$, absolute neutrophil count $>1500/\text{mm}^3$, and platelet count $>100\,000/\text{mm}^3$.
29. Chronic use of opiates or opioids (including long-acting opioid medication) within 90 days of study drug administration.
 - a. Intermittent short-term use (<1 week) of short-acting opioid medications for pain is permitted except within 2 days or 5 half-lives (whichever is longer) prior to any COA.
30. Chronic use of barbiturates, or hypnotics from 90 days prior to study drug administration.
 - a. Intermittent short-term (<1 week) use of buspirone or short-acting hypnotic medication for sleep or anxiety is allowed except within 2 days or 5 half-lives (whichever is longer) prior to any clinical outcome assessment.

Part 1 (Treatment Period) – Exclusion criteria applicable to those US, UK, or Canadian participants participating in the optional WLA only:

1. Has clinically significant vision impairment (corrected vision is acceptable).
2. Has clinically significant hearing impairment (use of hearing aids is acceptable).

